VA Office of Research and Development Results Record C0239-R

Title: Randomized Trial Comparison of Ototoxicity Monitoring Programs

ClinicalTrials.gov identifier: NCT02099786

Protocol; Document Date: 9-29-17

Experimental Methods

A. Subjects.

A1. Subject Recruitment: An estimated 320 patients from VA Portland Health Care System (VAPORHCS) receiving chemotherapy will be identified by a search of the upcoming chemotherapy unit appointment list, pharmacy list or by oncology referral including verbal referral and encrypted email. Additionally, approximately 120 healthy control subjects (Veterans and non-Veterans) not administered chemotherapy will also be recruited at the VAPORHCS from posted recruitment advertisements and from the NCRAR database of Veterans willing to participate in future hearing research projects. Potential chemotherapy patients will be accessed using electronic medical records (CPRS) to determine the diagnosis and treatment plan and to search for exclusionary criteria. If the potential subject is not excluded based on initial CPRS search, oncology personnel will approach the potential subject to determine his/her willingness to learn more about the study after hearing a brief description. The Program Evaluation (PE) audiologist will then talk with the patient, offer a more thorough explanation of the study, including the necessity for duplicate testing. If the potential subject remains interested in the project, informed consent will be obtained including an explanation of the goals of the study, requirements of the study protocol and the potential risks and benefits to the subject.

Initial testing to establish inclusion in the study and to provide the first PE will be done in a quiet area. After the evaluation, if the subject has met all further inclusion criteria, the subject will be randomized to a treatment arm: Standard of care (SOC) or Comprehensive Ototoxicity Monitoring Program for VA healthcare (COMP-VA). Study personnel will then be informed that a subject has been consented, tested, and assigned to a study arm and is ready to receive a baseline evaluation.

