C2a. Distortion Product Otoacoustic Emission Instrumentation for COMP-VA: Either the OtoID-based DPOAE testing (or cart system) can be used to collect DPOAEs.

C3. Other data to be gathered on study participants with cancer: Additional information obtained on each subject from the electronic medical records (CPRS) will be entered into the database, maintained by by study team members including a biostatistician and research assistant(s). Information to be obtained will include patient factors such as name, gender, age, type of cancer and staging, drug treatment variables such as cisplatin dose and dosing (intensity) and concomitant radiation dose and doublet medication and other information related to treatment and patient factors as required to accomplish the study goals. CPRS clinical progress notes will be monitored by a study team member on each subject (estimated n=80/yr) entered into either study arm in order to obtain Audiology Service utilization **for up to one year** post-randomization. In addition, in order to get a less biased estimate of audiological services utilization rates, an historical cohort comprised of all patients identified as receiving cisplatin approximately 3 years prior to the initiation of the study will be searched in CPRS and the cancer registry for audiological services used (estimated n=220 pts). We estimate approximately 300 patient records may be accessed to complete this search. These data may be combined with data from other studies done by these investigators in an IRB-approved manner.

A study team member may request providers' feedback in the form of a simple checklist (Oncology Practitioner Survey) provided to them at each treatment interval by a study team member.

We may also survey practitioners (oncologists, nurses, and audiologists) to assess their beliefs about ototoxicity monitoring practices using an anonymous beliefs questionnaire (i.e., no PHI or PII). This survey will be made available at 2 intervals.

In order to establish a benchmark for relapse-free survivorship from which to compare COMP-VA subjects' survivorship, we will be evaluated survivorship of Veterans with a diagnosis of cancers treated with cisplatin using the VA Cancer Registry (or other) which follows Veterans treated in VA for 5+ years following treatment. We will follow current study participants for cancer survivorship for approximately 2-3 years depending on enrollment date and resources available to do so.

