VA Office of Research and Development Results Record C0239-R

Title: Randomized Trial Comparison of Ototoxicity Monitoring Programs

ClinicalTrials.gov identifier: NCT02099786

Outcomes and Statistical Plan; Document Date: 9-29-17

Outcomes and Statistical Plan

Outcome Measures

The following outcomes were evaluated as a function of treatment arm.

1. **Hearing tests.** Rates of ototoxicity were evaluated using two criteria: (i) Ototoxic hearing shifts meeting the ASHA 1994 definition 20dB shift at one frequency; 10 dB shift at two consecutive frequencies or loss of response at three frequencies. (ii) Ototoxicity meeting the Cancer Institute Common Terminology Criteria for Adverse Events (CTCAE) Grade 1 or greater toxicity [hearing shift of 15-25 dB averaged at 2 contiguous test frequencies in at least one ear].
2. **Audiology rehabilitation service use.** This included: (i) service utilization to issue new hearing aids to subjects who were not hearing aid users at baseline; and (ii) technology update or hearing aid adjustment for previous hearing aid users. CPRS progress notes were monitored by the NCRAR Research Audiologist on each subject enrolled in the study in order to determine audiology rehabilitation service use for one year post-randomization. All audiology clinic visits were recorded by date and type of visit. Additionally, subjects were queried about aural rehabilitation service at each PE and interim phone calls.
3. **Quality of life measures.** Differences in the HHIA questionnaire score (or HHIE score as appropriate depending on the age of the subject) at PE 3 were evaluated.
4. **Survivorship** among subjects was also evaluated, defined as differences in rates of death during the study period.

Hypotheses to be Tested and Statistical Plan

1. *Use of COMP-VA will improve patients' hearing and quality of life outcomes without diminishing chances for survival.* Simple analysis will entail computing odds ratios and contrasting these between the COMP-VA and SOC groups. We will also fit a logistic regression model to the probability of ototoxicity (separately modeled for ASHA and CTCAE grade 1 or

greater) with randomization group assignment as predictor. *We anticipate that hearing loss progression will be less among COMP-VA subjects, meaning that, the COMP-VA group will have smaller 35 day and 1 year post-randomization hearing shifts compared to SOC patients.*

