2. *We hypothesize that COMP-VA will minimize some of the adverse effects of cisplatin treatment on Veterans' hearing-related quality of life, either through treatment modifications to diminish cisplatin-induced hearing loss or effective post-chemo audiological service delivery to limit the ill-effects of any pre-existing, new or worsened communication deficit.* We will conduct a contrast of perceived hearing handicap (HHIE or HHIA questionnaire administered at 1 year post-randomization), between patients randomized to COMP-VA and SOC. We will conduct a t-test with randomization arm as the contrast to test the importance of COMP-VA on perceived quality of life outcomes.

3. *Compared with patients randomized to SOC, patients randomized to COMP-VA will use Audiology rehabilitation services at a higher rate because of their greater awareness of new, increased or pre-existing communication deficits.* To test this hypothesis, we will contrast the probability of one or more audiology clinic rehabilitation visits using logistic regression with group membership as a factor.

4. *We anticipate that cisplatin patients given the COMP-VA intervention will fair no worse than SOC patients in terms of their survival.* This component of the study is framed as a non-inferiority trial. i.e. we require sufficient evidence to reject the null hypothesis that COMP-VA patients have lower one-year survival rates than patients treated under SOC. Analysis for non-inferiority trials using survival outcomes have been described and are easily computed using logistic regression output. We will require a non-inferiority margin of no more than 1.1 mortality odds among COMP-VA patients relative to SOC patients. From an analytical

perspective this means that the upper 95% confidence bound for the fitted odds ratio must be less than 1.1 to reject the null hypothesis that COMP-VA induces extra mortality risks.

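### SAP item 4 states its survival null as any extra mortality, but the 1.1 margin and rule test only an odds ratio of 1.1 or more, so a pass can be worded too strongly

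*SAP*

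**What the plan says.** The SAP, under Hypotheses to be Tested and Statistical Plan, item 4, treats survival as a non-inferiority comparison analysed by logistic regression. It words the null twice.

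- As the aim of the test: the trial needs enough evidence to "reject the null hypothesis that COMP-VA patients have lower one-year survival rates than patients treated under SOC".
- As part of the decision rule, which concerns the upper limit at the 95% level: "confidence bound for the fitted odds ratio must be less than 1.1 to reject the null hypothesis that COMP-VA induces extra mortality risks".

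Between the two it sets the margin: "We will require a non-inferiority margin of no more than 1.1 mortality odds among COMP-VA patients relative to SOC patients".

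The test supports item 1 of the same section, which says COMP-VA will improve patients' "hearing and quality of life outcomes without diminishing chances for survival". Under Outcome Measures, item 4, the SAP describes the survival outcome as "defined as differences in rates of death during the study period", without the one-year limit used in the hypothesis.

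**The concern.** Neither wording of the null contains the margin. Lower survival, or extra mortality risk, with no amount attached means a mortality OR above 1. To reject that null, the upper bound would have to lie below 1.0. The stated rule asks only for a bound below 1.1, so it rejects a narrower null: OR of 1.1 or more.

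The two differ for one set of results, those with an upper bound from 1.0 up to 1.1. There the SAP's sentence says that extra mortality risk has been rejected, while the interval still contains odds ratios above 1. What is at stake is the safety statement attached to COMP-VA. The claim that survival is not diminished would rest on a result that excludes only increases of 10% or more in the odds of death.

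**Working it through.** The documents give no expected mortality and no derived figure for this test, so there is no plan figure to reproduce. The mismatch follows from the text alone; the numbers below only show its size.

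**Inputs.** From SAP item 4: margin 1.1, rule (upper 95% bound below 1.1), logistic regression, one-year survival. Assumed: 160 per arm, and one-year SOC mortality of 10% to 50%. Protocol A1 gives "An estimated 320 patients from VA Portland Health Care System (VAPORHCS) receiving chemotherapy", but as patients to be identified, not as the number randomized, and no allocation ratio is stated. A 1:1 split would give 320 / 2 = 160. The SAP does not say whether the 95% bound is one- or two-sided, so both are shown.

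**Step 1: one result worked through.** Take 48 SOC deaths of 160 (30%) and 35 COMP-VA deaths of 160.

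- OR = (35/125) / (48/112) = 0.2800 / 0.4286 = 0.653; ln OR = -0.4257
- SE = sqrt(1/35 + 1/125 + 1/48 + 1/112) = 0.2576
- Two-sided 95% limits: exp(-0.4257 ± 1.960 × 0.2576) = 0.39 to 1.08
- One-sided 95% upper bound: exp(-0.4257 + 1.645 × 0.2576) = 0.998

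With the two-sided interval this passes (1.08 is below 1.1), and increases in the odds of death of up to 8% are not excluded. With the one-sided bound the same counts do exclude any increase, so this example shows the fault only under the two-sided reading.

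**Step 2: the affected counts against 48 SOC deaths.**

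| COMP-VA deaths | OR | Upper bound, two-sided 95% | Upper bound, one-sided 95% |
|---|---|---|---|
| 32 | 0.58 | 0.98 | 0.90 |
| 33 | 0.61 | 1.01 | 0.93 |
| 34 | 0.63 | 1.05 | 0.96 |
| 35 | 0.65 | 1.08 | 0.998 |
| 36 | 0.68 | 1.12 | 1.03 |
| 37 | 0.70 | 1.16 | 1.07 |
| 38 | 0.73 | 1.19 | 1.10 (1.103, misses) |

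The wording is too strong at 33 to 35 deaths (two-sided) or 36 to 37 deaths (one-sided). At 32 or fewer (two-sided) or 35 or fewer (one-sided) the upper bound is below 1.0, and the SAP's conclusion is supported as written.

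**Step 3: size of the margin in absolute terms.** With odds(p1) = 1.1 × odds(p0), the excess is p1 - p0. At p0 = 30%: 1.1 × 0.4286 = 0.4714, so p1 = 0.4714 / 1.4714 = 32.0%, an excess of 2.0 points. At SOC mortality of 10, 20, 30, 40 and 50% the excess is 0.9, 1.6, 2.0, 2.3 and 2.4 points.

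**Step 4: is the rule sound for the null it really tests?** In large samples P(pass | OR) = Φ((ln 1.1 - ln OR)/SE - z). At OR = 1.1 this is Φ(-z): 2.5% for the two-sided bound and 5.0% for the one-sided bound. Exact enumeration of two binomial counts at 160 per arm, over 10% to 50% SOC mortality, gives 2.3% to 2.6% and 4.8% to 5.5%. The rule is therefore close to a nominal test of OR of 1.1 or more.

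**The case against.** The strongest reply is that the paragraph resolves itself. It names a non-inferiority trial, sets the margin, and then presents the rule as what the margin means in analysis. In that setting the two null wordings are shorthand for worse by at least the margin, and no analyst would run a different test. This stands as to the test. It does not mend the conclusion, because the sentence that says what a pass proves omits the margin.

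A second reply is that the affected band is narrow. It is. Under the assumptions above and equal true mortality, an upper bound from 1.0 up to 1.1 occurs in about 1.7% to 4.0% of trials (two-sided) or 3.2% to 6.8% (one-sided). In the worked example the estimates in the band favour COMP-VA. That is why the point is minor.

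A reader might also infer more than the documents support:

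- *That no pass can support a claim of no extra mortality.* Step 2 shows otherwise: a bound below 1.0 excludes any increase.
- *That the plan lets a missed rule count as reassurance.* Item 4 puts the burden of proof on COMP-VA, and neither document labels a miss harmless. Spelling out how to read a miss would be added detail, not the repair of an error.
- *That the survival test contradicts the longer follow-up in Protocol C3.* That section says "We will follow current study participants for cancer survivorship for approximately 2-3 years depending on enrollment date", but in a paragraph about a registry benchmark for relapse-free survivorship. It does not define the window of the randomized one-year comparison.

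**Conclusion.** The point holds as a minor fault in the stated null and in the conclusion drawn from a pass. The rule tests OR of 1.1 or more, while the text claims rejection of any extra mortality. The claim goes too far only when the upper bound lies from 1.0 up to 1.1. At the margin, the excess at issue is 0.9 to 2.4 percentage points of mortality, given an assumed SOC mortality of 10% to 50%.

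The mismatch itself depends on no assumption. The example counts depend on 160 per arm, 48 SOC deaths and the sidedness of the bound. It would be wrong to infer that the test is invalid: against OR 1.1 its error is near nominal. How likely the trial is to meet the rule is a separate question, which this point does not address.

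**What to change.** Rewrite SAP item 4 as follows.

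1. State H0 as one-year mortality OR (COMP-VA relative to SOC) of 1.1 or more, against H1 of OR below 1.1.
2. State that a pass shows, at minimum, that an increase of 10% or more in the odds of death is excluded. Reserve a conclusion of no extra mortality for an upper bound below 1.0, and word the survival part of item 1 to match.
3. Report the one-year mortality OR and risk difference with two-sided 95% confidence intervals, whatever the outcome.
4. In the same edit, say whether the bound in the rule is one- or two-sided, and use the one-year window in Outcome Measures item 4 as well.

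The cost is SAP wording and one added estimate, the risk difference with its interval. No new patients or data are needed, and the decision rule is unchanged apart from the sidedness being stated. The downside is that the survival claim becomes slightly less favourable when the upper bound lies from 1.0 up to 1.1.
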